### 3.1.2 Secondary

Quantify the behavioral, social, and clinical factors that mediate and moderate the efficacy of the HealthMindr app on the rate of PrEP uptake.

Conduct in-depth interviews to assess how the app promoted PrEP uptake, unmet needs of men who did not start PrEP, and how repeated app interactions might further PrEP uptake.

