#### 12 STATISTICAL CONSIDERATIONS

# 12.1 Study Hypotheses

- 1) The rate of PrEP uptake will be higher among men provided with the HealthMindr app compared to men provided with standard of care.
- 2) Access to additional HIV prevention services available in the HealthMindr app will result in reductions in risk behaviors or greater access to HIV testing services, which are associated with PrEP uptake.
- 3) Individual, social, and community characteristics of participants will be associated with PrEP uptake among participants provided access to the HealthMindr app.

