#### 12.3 Final Analysis Plan

The main analysis will use four standard survival analysis techniques to compare the rate of PrEP initiation by study arm and estimate the size and statistical significance for observed differences. This approach will account for loss-to-follow-up, study termination due to competing events (e.g., HIV seroconversion), and other forms of censoring. The first analysis will use Kaplan-Meier methods to characterize the empirical survival distribution, which here is the timedependent probability of remaining PrEP uninitiated over follow-up. This method will yield estimates of the median time to PrEP initiation and cumulative incidence with 95% confidence intervals. Second, log-rank or related (e.g., Harrington-Fleming) statistical tests will be used to test the null hypothesis of no difference in rates of PrEP initiation by study arm, with a cutoff p value of 0.05 used to determine significance. 52 Third, a Cox proportional hazards model will be used to estimate the hazard ratio associated with study arm to characterize the strength of causal effect of use of the app. The primary model will only include an independent exposure variable for the study arm as randomized (i.e., standard intent-to-treat analysis), but secondary models may include covariates (including those related to the four domains along the PrEP continuum) for which there is descriptive evidence of residual imbalance after randomization. Fourth, parametric survival models (e.g., under exponential or Weibull distributional assumptions) will be used to characterize the rate of PrEP initiation overall and by study arm.

Mediation Analysis: This analysis will examine how study arm assignment may lead to intermediate effects, such as greater access to HIV testing or decreased risk behavior, which themselves are associated with the primary effect of PrEP initiation. Using the difference method for a set of Cox proportional hazards models similar to those in the Aim 2 analyses, log coefficients for the indirect effects will be subtracted from log coefficients for the direct effect to estimate the size of the mediation. Mediators will be selected on the variables known to be associated with the 4 domains of the PrEP continuum (including awareness, access, and engagement with HIV prevention services), and changes in risk behaviors resulting from app utilization.

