Moderation Analysis: This analysis will examine how attitudes and beliefs about PrEP, as well as individual, social, and community characteristics can moderate the effect of the app on PrEP initiation. Examples of moderators include perceived benefits of PrEP use, self-assessed

vulnerability to HIV, perceived advantages to meeting partners if currently taking PrEP, and social support for PrEP use within one's social network. Demographic factors such as age, race/ethnicity, and geographic setting will also be critical moderators. Although the distribution of these factors will be balanced across study arm with randomization, they may have effects on the level of engagement in the app (i.e., post-randomization treatment adherence) that itself will influence the rate of PrEP initiation. Given this causal model, we will use instrumental variable analyses to estimate the effect of optimal app use on PrEP initiation given measured and unmeasured moderators.

In-Depth Interview Data Analysis: All IDIs will be digitally recorded, transcribed verbatim, and de-identified. Transcripts will be entered into MAXQDA, which facilitates the processes of coding, annotating, and retrieving text such that analysts may note patterns in the textual data across themes. Data analyses will be conducted using a phenomenological inquiry framework. Phenomenology is focused on describing what a given group of people have in common as they experience a phenomenon, and is an inductive analytic approach that allows the patterns, themes, and categories of analysis to emerge from data. Data are then presented through textual phenomena descriptions based on summaries of experiences described by respondents. Composite descriptions offer explanation of underlying structures which exist across the respondents' experiences.

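### Aim 2 asks what moderates the app's effect, but Hypothesis 3 and the one method named for moderation target other quantities, and no arm-by-moderator contrast is specified

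*Combined protocol and SAP*

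**What the plan says.** Section 3.1.2 sets the secondary objective: "Quantify the behavioral, social, and clinical factors that mediate and moderate the efficacy of the HealthMindr app on the rate of PrEP uptake". The Protocol Summary lists the same objective as Aim 2.

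Three pieces of text bear on the moderation half of it.

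- **Hypothesis 3, section 12.1:** "Individual, social, and community characteristics of participants will be associated with PrEP uptake among participants provided access to the HealthMindr app".
- **Moderation Analysis, purpose (3.2.2 and 12.3):** the paragraph will examine how attitudes and beliefs, "as well as individual, social, and community characteristics can moderate the effect of the app on PrEP initiation". It gives examples of moderators, and in 12.3 it adds: "Demographic factors such as age, race/ethnicity, and geographic setting will also be critical moderators".
- **Moderation Analysis, method (same paragraph in both sections):** these factors may influence engagement with the app, and engagement may influence uptake. On that causal model, "we will use instrumental variable analyses to estimate the effect of optimal app use on PrEP initiation given measured and unmeasured moderators".

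The other models in the plan do not contain the contrast. For the Cox analysis in 12.3, "The primary model will only include an independent exposure variable for the study arm as randomized", and secondary models may add covariates "for which there is descriptive evidence of residual imbalance after randomization". The principal-stratification and dose-response analyses (8.1 and 12.2.1) concern adherence and engagement, and the second is confined to app users. Section 4 says only that the survey measures permit exploration of possible moderators.

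**The concern.** A moderator of efficacy is a factor across whose levels the app-versus-control effect differs. Showing that needs both arms at each level of the factor. Hypothesis 3 has no control arm, so a factor that raises uptake equally in both arms satisfies it without moderating anything. The instrumental-variable sentence names a different target again, the effect of using the app optimally, with the moderators entering as influences on engagement.

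An analyst who follows the text therefore has a correct statement of purpose, a hypothesis about prognosis and a method about app use, but no model for effect modification. The moderation half of Aim 2 could end without an answer. If the hypothesis were tested as worded, prognostic factors could be taken for moderators. The primary analysis is not affected.

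**Working it through.** **Inputs from section 12.2:** 438 app and 219 control men; uptake 9% against 2%; 4.5-fold hazard; alpha 0.05 (taken as two-sided); 20% annual attrition; stated power 91%. **Assumptions, because the documents give none:** a binary factor, split 50/50 or 30/70, with a hazard ratio of 2.0 or 2.5.

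**1. The plan's own figure.** Two-proportion power with 20% removed (350.4 and 175.2 men): pooled rate 0.0667, null SE 0.0231, alternative SE 0.0186. Φ((0.07 − 1.96 × 0.0231)/0.0186) = 90.9%. An exponential-hazard formula with 20% annual loss gives 91.5%. The stated 91% is reproduced.

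**2. Expected events.** A 4.5-fold hazard on a 2% control risk gives an app-arm risk of 1 − 0.98^4.5 = 8.7%.
- No attrition: 438 × 0.0869 = 38.1 app and 219 × 0.02 = 4.4 control events.
- All 20% removed: 30.5 and 3.5.
- Exponential loss: 34.2 and 3.9.

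**3. Why an association within the app arm is not moderation.** Take a factor that doubles uptake in both arms: app 6% and 12%, control 1.33% and 2.67%. The averages are the plan's 9% and 2%. Within the app arm the association is two-fold. The app's rate ratio is 6/1.33 = 4.5 at one level and 12/2.67 = 4.5 at the other, so on the ratio scale nothing is moderated.

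**4. How often an app-arm test would flag that factor.** Power = Φ(ln 2 × √(0.25 × events) − 1.96), 50/50 split.
- 30.5 events: Φ(1.914 − 1.96) = 48%.
- 38.1 events: Φ(2.139 − 1.96) = 57%.

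Simulation (6,000 trials, exponential times, one year, 20% annual loss, same hazard ratio in both arms) gave 49-50% at hazard ratio 2.0 and 72% at 2.5. In those trials an arm-by-factor Wald test rejected in about 1%, and some arm-by-factor cell had no events in about a third (32-36%).

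**5. What the interaction test can deliver.** SE of the log ratio of hazard ratios = √(sum of 1/events over the four cells).
- 50/50 split: 2 × √(1/38.1 + 1/4.4) = 1.01 to 2 × √(1/30.5 + 1/3.5) = 1.13.
- 30/70 split: 1.10 to 1.23.
- Power for a two-fold ratio, Φ(ln 2/SE − 1.96): 10% at SE 1.01, 8% at SE 1.23.
- Power for a 4.5-fold ratio: 23-32%.
- Ratio detectable with 80% power: about 17-24 (50/50) or 22-32 (30/70).

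These are large-sample approximations and are rough with about 4 control events.

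**6. Choice of scale.** With hazard ratio 2.0 in both arms and overall risks of 9% and 2%, exponential times give app risks of 6.1% and 11.9% and control risks of 1.3% and 2.7%. The risk differences are 4.8 and 9.2 points, so the interaction is 4.4 points although the hazard ratios are equal. At hazard ratio 2.5 it is 5.7 points. The SE of the risk-difference interaction is √2 × √(0.09 × 0.91/n₁ + 0.02 × 0.98/n₀):
- 197 and 98.5 men per cell (10% removed, roughly what 20% annual loss costs in follow-up): 3.5 points.
- 175.2 and 87.6 men per cell (all 20% removed): 3.7 points.

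**The case against.** The best defence is that the plan is under-specified rather than misdirected. The Moderation Analysis paragraph says outright that it is about moderation of the app's effect, and it names moderators. The instrumental-variable sentence deals with one pathway, through engagement, and is not said to be the only analysis. The mediation paragraph in 12.3 also mentions Cox models used for Aim 2, although mediation is itself part of Aim 2, so this shows little. Moderation is secondary, and with so few control events an interaction test would rarely find anything.

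Much of this stands as a limit on the point. A reader might infer that the plan commits to two moderation analyses, one of them an association test confined to the app arm, and so will report prognostic factors as moderators. The documents do not support that: the association is a hypothesis in 12.1, and no such test is laid out in 3.2.2, 12.2.1 or 12.3. The figure of about half of trials applies only if Hypothesis 3 is tested as worded.

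A reader might also infer that the instrumental-variable estimate averages over the moderators. The text does not say so. It says given the moderators, which could mean conditional on them, and the methods paper it cites cannot be consulted here.

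What does not stand is that this is only missing detail. A hypothesis and a method are both stated, and each targets something other than the aim. Low power is a reason to label the results exploratory; it does not turn an app-arm association into a test of moderation.

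**Conclusion.** The point holds in this form: the purpose is stated correctly, but Hypothesis 3 is worded as prognosis within the app arm, the only named method yields an effect of app use, and no contrast of the app's effect across levels of a factor is specified.

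Conditional on testing Hypothesis 3 as worded, a purely prognostic factor with hazard ratio 2.0 would reach significance in about half of trials. That rests on the plan's rates and on an assumed 50/50 factor acting equally on the hazard in both arms. It would be wrong to go further and call every such factor a non-moderator on all scales, since the same factor produces a risk-difference interaction of about 4.4 points. The scale has to be chosen in advance. The change should be made before analysis.

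**What to change.** 1. **Section 12.1:** reword Hypothesis 3 as *the effect of the app on PrEP uptake differs by baseline characteristics*.
2. **Sections 3.2.2 and 12.3:** specify an arm-by-baseline-moderator interaction in all randomised men. Use baseline-survey values only, because perceptions and beliefs are asked again in the quarterly surveys (6.1.1) and later values may already reflect the app.
3. **Main scale:** the Cox hazard ratio, matching the primary model. Report the ratio of hazard ratios with its confidence interval, by a penalised or exact method where a cell has few or no events.
4. **Supplement:** 12-month risk differences by level, with a note that equal hazard ratios in both arms still produce a risk-difference interaction.
5. **Instrumental-variable analysis:** move it to the adherence and dose-response analyses in 12.2.1, labelled as an effect of app use.

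The cost is SAP wording and a few extra models on data already collected, with no change to sample size, procedures or the primary analysis. The downside is imprecision: power of about 8-10% for a two-fold interaction, and a risk-difference interaction with a 95% half-width of about 7 points (1.96 × 3.5 = 6.9; 1.96 × 3.7 = 7.3). The results must be labelled exploratory.

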#### 13 SOURCE DOCUMENTS AND ACCESS TO SOURCE DATA/DOCUMENTS

Study staff will maintain appropriate medical and research records for this study, in compliance with ICH E6, Section 4.9 and regulatory and institutional requirements for the protection of confidentiality of subjects. Study staff will permit authorized representatives of NIDA and regulatory agencies to examine (and when required by applicable law, to copy) research records for the purposes of quality assurance reviews, audits, and evaluation of the study safety, progress and data validity.

#### 14 QUALITY CONTROL AND QUALITY ASSURANCE

The main sources of possible data entry errors will lie with the matching of study ID numbers and participant identifying information and with capturing of participant information from mail inspecimens. This risk will be mitigated by identifying any mail-in specimen with a possible discrepancy in linking with study ID; such specimens will not be processed and participants will be requested to provide a new specimen. For app-based and survey-based data, the participant identifiers are associated with the electronic record automatically, so the chance of problems with attribution of responses to the incorrect participant is very small.

For study IDs, the files linking the study ID and identifying information will be generated through a SAS program that retrieves data entered by the participant at the time of enrollment.

For mailed-in specimens, all specimen tubes will be labelled with a unique ID number, which will be the same for all tubes in one specimen collection kit, i.e. the box ID. Participants will be asked to register this box ID using a unique URL linked to their study ID. This will allow linkage of specimen test results back to the correct participant.

# 14.1 Recontacting Past Participants

Participants who reported PrEP initiation on a monthly check-in survey but not a quarterly survey (primary study outcome) will be contacted for clarification. Only the participants who previously provided consent to be recontacted will receive a message. A \$20 compensation in the form of electronic gift code will be given to those participants who respond.

Voicemail: Hi, this is [insert your name] calling from Emory with the HealthMindr study. You have reported starting PrEP during our research study, but you also reported that you have not started PrEP in surveys afterwards. I was hoping to verify some information from your time in the study. You are eligible to receive additional compensation for your response. You can call us back at [phone number]. Or feel free to text me and let me know what the best time is for a call. Thank you!

Phone Script: Hello, may I speak with [PARTICIPANT'S NAME]? My name is [insert your name]. I am with Emory working on the HealthMindr study. You have reported starting PrEP during our research study, but you also reported that you have not started PrEP in surveys afterwards. According to your survey, you reported PrEP usage in [MONTH/YEAR]. Is this correct? Did you stop taking PrEP any time after?Thank you for your clarification. Also for the compensation, we will send you a \$20 gift code. Do you have a preferred store? We have gift codes from Amazon, Target and Walmart.That is all the questions I have and thank you for participating in our research study!

Text Message: Hello! This is [NAME] from the Emory HealthMindr study. We were hoping to get you on a call for a few minutes to to verify some information from your time in the study and you will be compensated for your time. What time works best for you for a short phone call?

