#### 6.1.1 Acquisition

After completing the eligibility screener and informed consent (Appendix B), participants will be directed to a link to authenticate their smartphone and download the HealthMindr App from either Google Play or Apple App Store. All participants will view the same app shell and complete the baseline survey in the app. However, once randomized, the app for those marked as intervention will open up to show all HealthMindr app capabilities. The app information will cover the importance of testing, links to HIV prevention resources, resources to locate HIV testing and PrEP services, the SAMHSA substance abuse treatment resource locator, and other prevention information specific to their area. The app for the control arm will allow study staff to interact with them via the SMART system. The control-arm app will display a study event timeline but none of the HIV prevention information contained in HealthMindr app.

The HealthMindr application will prompt the intervention participants to complete a brief PrEP assessment (monthly). Any notifications directed to a phone's lock screen or to a participant's SMS/text message account can be partially viewed by unauthorized users of the phone and will be generic text (e.g., "You have a message waiting for you."). To ensure that app notifications protect the privacy and discretion of participants, all app and text notifications will be stated generally, with no reference to the content of the message, the nature of the message, the content of the app in general, the name of the study, or any reference to HIV, STI or MSM. The lock screen banner notification will indicate only that the notification is for the HealthMindr app. SMS/text message notifications will similarly alert participants that a new message is available in HealthMindr. Absolutely no content referring to sensitive topics will be exposed without directly entering the app. The same notification format will be used for both intervention and control groups.

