#### 9.1.1 Adverse Events

- 1. Participant report of loss of confidentiality through the app or its functions
- 2. Participant report of loss of confidentiality through delivery of prevention supplies or commodities
- 3. Participant report of access by others to protected health information through the app or study procedures.
- 4. Participant report of disclosure of status as a research participant due to study-related reminders (from app, phone calls, emails, or text messages).
- 5. Participant report of discomfort or injury due to use of provided specimen collection materials (e.g., finger stick for syphilis testing, self-administered rectal swab or pharyngeal swab).
- 6. Disclosure of personal information about health, sexuality or sexual practices that results in physical violence or threat of violence.
- 7. Disclosure of personal information about health, sexuality or sexual practices that results in adverse effects on employment

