#### Study procedures

We will collect multiple means of contact with participants at the study visit. For each means of permitted contact, we will leave a generic message about participation in a health research survey at that phone/email/cell phone, etc. Standardized scripts for phone and email contact will

be used (uploaded in the eIRB system for review). Participants are offered the option to receive STI testing results by email or text message; for those who so choose, the results messages will not identify the type of testing, the nature of the study, or the specific test names. Scripts for the return of results by email or text message are included in the "Miscellaneous Documents" section of the eIRB forms.

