To minimize risks to confidentiality, we will provide study data with all appropriate physical and operational security protections. Paper-based data will be stored in a locked cabinet in a locked office, and all data files will have encryption and strong password protection. Access to data will be on a role-based standard; only those study staff, such as principal and co-investigators, data managers, data analysts, study staff (public health program associates and assistant or associate directors of research), and graduate research assistants, who require access to identifying data to complete their study-related roles will be allowed access. Any photographs (i.e., PrEP prescriptions or bottle labels) will be sent to study staff securely through the app. SurveyGizmo, the electronic platform for self-interview, has a HIPAA business partner agreement with Emory. All study staff will complete CITI course modules on human subjects research ethics, socio-behavioral research, and good clinical practice (GCP), will be trained in security and confidentiality procedures, and will sign a confidentiality agreement before receiving access to any participant data. Any breaches in confidentiality will immediately be reported to the PI and to the IRB. Based on the PI and IRB's recommendation, staff may be retrained or receive disciplinary action.

Study staff will follow procedures to minimize indirect disclosure that a participant is participating in an HIV-related research study, or a study that enrolls MSM. For each mode of contact information, including email, telephone, text, and voicemail, we will ask specifically whether anyone else potentially has access to that mode of communication, and if it is acceptable to leave a non-specific message about participation in a health study. No study-related messages to the participant will ever mention HIV prevention or the nature of the research study. Additionally, all scripts for email, text message, and telephone contact with participants will be reviewed and approved by the Emory IRB before being used for contact with participants.

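### The recontact voicemail in Section 14.1 mentions PrEP, which Sections 15.6 and 16.2 do not allow in a message left for a participant

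*Combined protocol and SAP*

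**What the plan says.** Section 14.1 sets out how staff recontact men who reported starting PrEP on a monthly check-in but not on a quarterly survey, the latter being the primary outcome source. Only men who consented to be recontacted are approached. The section supplies three scripts.

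- **Voicemail.** The caller is "calling from Emory with the HealthMindr study. You have reported starting PrEP during our research study". The same sentence continues by saying that the man also reported, in later surveys, that he had not started. PrEP is named twice.
- **Live call.** The caller asks for the participant by name, introduces the study, and then recites the same two reports.
- **Text message.** It names the study and asks for a time to talk. It does not mention PrEP.

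Two other sections govern what may be said in messages. Section 16.2 opens its contact rule with its scope: "For each mode of contact information, including email, telephone, text, and voicemail". Staff are to ask whether anyone else could have access to that mode, and "if it is acceptable to leave a non-specific message about participation in a health study". It then states without qualification: "No study-related messages to the participant will ever mention HIV prevention or the nature of the research study". Section 15.6, under Study procedures, says that for each permitted means of contact "we will leave a generic message about participation in a health research survey at that phone/email/cell phone".

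Section 6.1.1 has its own rule for app and text notifications. It excludes the study's name, but then has the lock-screen banner identify the HealthMindr app and adds: "SMS/text message notifications will similarly alert participants that a new message is available in HealthMindr".

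**The concern.** Unwanted disclosure is the harm this trial guards against most visibly. The stated aim in Section 16.2 is to keep others from learning indirectly that a man is in an HIV-related study or one that enrolls MSM. The same section describes generic push notifications and a PIN for sensitive in-app messages. A recorded message about PrEP bypasses those safeguards.

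The conflict also leaves staff with no compliant course. Someone who reads out the Section 14.1 voicemail departs from Sections 15.6 and 16.2. Someone who keeps to those sections departs from the script in 14.1. Section 16.5 requires protocol deviations to be reported, and either course could count as one. A disclosure, once made, cannot be reversed.

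**Working it through.** No arithmetic applies to the core point, so the check is a comparison of the texts.

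1. **Is voicemail within the rule?** Yes. Section 16.2 lists it by name alongside email, telephone and text.

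2. **Does the script mention HIV prevention?** Yes. Section 15.1.2 describes pre-exposure prophylaxis as being for HIV prevention, and the script names PrEP twice. This alone conflicts with the promise in Section 16.2.

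3. **Is the script generic in the sense of Section 15.6?** No. That section describes a message about taking part in a health survey. The script recites the content of the man's own survey answers.

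4. **Is there an exemption for recontact?** None appears in the supplied text. Neither Section 15.6 nor Section 16.2 limits its rule to men still in follow-up.

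5. **Does consent to recontact remove the conflict?** No. As Section 14.1 describes it, that consent settles who may be contacted. The permission described in Section 16.2 is for a non-specific message only.

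6. **Does IRB approval of scripts remove it?** No. Section 16.2 requires that approval in the same paragraph as the content rule. Approval does not make two incompatible instructions compatible.

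7. **Is the PrEP wording needed to obtain a call back?** The protocol's own text script suggests not, since it asks for a call without it.

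8. **Which listed adverse event applies?** Item 3 of Section 9.1.1 is the closest match: a participant's report that other people gained access to his protected health information by way of the app or the study's procedures. Items 6 and 7 (disclosure leading to violence or threats, or to adverse effects at work) are possible consequences. Item 4 fits less well, because it concerns reminders and a one-off clarification call is arguably not a reminder.

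**The case against.** The strongest reply accepts the voicemail conflict and disputes what might be built on it. Several stronger readings are tempting, and the documents do not support them.

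- **That the script causes harm.** Harm follows only if someone other than the participant hears the recording. Section 16.2 has staff ask who else has access to each mode of contact, and item 3 of Section 9.1.1 arises only when a participant reports it. The supportable statement is that the script can expose men to disclosure.
- **That the script says the man started PrEP.** It recites two conflicting reports and asserts neither.
- **That every voicemail discloses PrEP use, or that about 44 men are affected.** The first treats a recording as disclosure to a third party and a discordant report as use. The second might be inferred from the planning rates in Section 12.2: 438 × 0.09 = 39.4 and 219 × 0.02 = 4.4, together 43.8. That is a count of expected initiators. The recontacted group is men with discordant reports who also consented to recontact. It could be smaller than 44, or larger if many monthly reports are mistaken.
- **That the live call and the text message break the same rules.** The rules are aimed mainly at messages that are left, and the live script first asks for the participant by name. An identity and privacy check there is a sensible improvement, but its absence is not a clear breach. The text script mentions neither PrEP nor HIV.
- **That naming the study is itself barred.** Section 16.2 bars mention of HIV prevention and of the nature of the study, not its name. The bar on the name is in Section 6.1.1, applies to notifications, and is undercut there by the display of HealthMindr.

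The enrolment consent text (Appendix B) and the contact scripts held in the IRB system are not in the supplied text, so a broader permission cannot be ruled out. It would still leave Section 14.1 at odds with Sections 15.6 and 16.2 as written. None of these replies answers the voicemail conflict.

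**Conclusion.** The point stands in a narrow form, and it should be corrected before the script is used. The voicemail in Section 14.1, read out as written, breaches the participant-protection rules in Sections 15.6 and 16.2 and can expose men to disclosure of health information. How many men are affected cannot be derived from the documents.

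The conclusion rests on two readings: that a recontact voicemail is a study-related message, and that PrEP counts as HIV prevention. The protocol's own wording supports both. Sample size, power, alpha and the analysis method are unaffected. The inconsistency in Section 6.1.1 over the study name is real, but it is separate and minor.

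**What to change.** Replace the Section 14.1 voicemail with the generic form that Sections 15.6 and 16.2 already call for: a call from the university about a health study, and a request to call back, with no PrEP or survey content.

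As a low-cost safeguard, move the PrEP wording in the live phone script to after the caller has confirmed who is speaking and that he can talk privately.

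Separately, reconcile Section 6.1.1 so that it either allows the HealthMindr name in both lock-screen banners and text alerts or removes it from both.

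The cost is a script amendment with IRB review, and possibly a slightly lower call-back rate to a vaguer voicemail. The calls exist to clarify discordant reports of PrEP initiation, so fewer call-backs would leave somewhat more of those reports unresolved. The documents give no figure from which to size that loss.
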